3.0	[REDACTED]	
Section 4.3 updates:
 
 • Updated section 4.3 to correctly state up to 360 subjects will be enrolled with 330 to complete, not 360 / 306. 
Section 3.4, 4.3 updates:
 
 • Modified the number of sites to read 18-20, instead of up to 18. 	
 • Accuracy 	17 Mar 2022

Clinical Study Protocol

Johnson & Johnson Vision Care, Inc.

SYNOPSIS

Protocol Title	Clinical performance of senofilcon A investigational lens
Sponsor	JJVC, [name]
Clinical Phase	Clinical trial phase: Claims Design control phase: Phase 3
Trial Registration	This study will be registered on ClinicalTrials.gov by the Sponsor
Test Article(s)	Investigational Products: senofilcon A prototype as the Test lens Approved Products: Dailies Total 1 as the Control lens
Wear and Replacement Schedules	Wear Schedule: daily wear Replacement Schedule: daily disposable
Objectives	Primary Objectives: This study is being conducted to evaluate the clinical performance of an investigational soft contact lens against the clinical performance of a marketed product.
Study Endpoints	Primary endpoint(s): Subjective responses concentrated on comfort towards the end of the day. Secondary endpoint(s): Subjective responses concentrated on digital device use, night driving, and all day comfort. Other observations: Subjective responses concentrated on other aspects of vision, comfort, and/or handling.
Study Design	This study is a controlled, randomized, subject-masked, 2-arm parallel, 2-week dispensing, bilateral evaluation where the study lenses are worn for a minimum of 5 days per week and 6 hours per day. There will be a total of 2 visits: 1. Visit 1: Screening, baseline evaluation and lens fitting. 2. Visit 2: Follow-up evaluation, final evaluation. See the flow chart at the end of the synopsis table for the schematic of the study visits and procedures of main observations (Figure 1).
Sample Size	Up to 360 subjects will be enrolled to complete approximately 330 (approximately 165 in each arm).

Clinical Study Protocol
Johnson & Johnson Vision Care, Inc.

Study Duration	Once enrolled, each subject will be in the study for 2 weeks. The enrollment period is 4 weeks per site, making the entire study duration approximately 6 weeks.
Anticipated Study Population	The study will enroll habitual wearers of spherical silicone hydrogel contact lenses, daily wear reusable and daily disposable. Subjects may be of any race or ethnicity that meet the eligibility criteria.
Eligibility Criteria - Inclusion	
Potential subjects must satisfy all of the following criteria to be enrolled in the study:
 
Inclusion Criteria after Screening
 
The subject must:
 
 1. Read, understand, and sign the STATEMENT OF INFORMED CONSENT and receive a fully executed copy of the form. 2. Appear able and willing to adhere to the instructions set forth in this clinical protocol. 3. Be between 18 and 39 (inclusive) years of age at the time of screening. 4. By self-report, habitually wear spherical soft silicone hydrogel contact lenses in both eyes in a daily wear or daily disposable wear modality (i.e. not extended wear modality). Habitual wear is defined as a minimum of 6 hours of wear per day, for a minimum of 5 days per week during the past 30 days. 5. Have a habitual contact lens prescription that is current within the prior 6 months, and they must have worn that prescription for at least 2 weeks prior to entering the study. 6. Possess a wearable pair of spectacles that provide correction for distance vision. 
Inclusion Criteria at Baseline Evaluation
 
 7. The spherical equivalent of the subject's vertex-corrected distance refraction must be between -1.00 and -6.00 DS (inclusive) in each eye. 8. The magnitude of the cylindrical component of the subject's vertex-corrected distance refraction must be between 0.00 and 1.00 DC (inclusive) in each eye. 9. The best corrected, monocular, distance visual acuity must be 20/25 or better in each eye.

Clinical Study Protocol

Johnson & Johnson Vision Care, Inc.

Eligibility Criteria – Exclusion	
Potential subjects who meet any of the following criteria will be excluded from participating in the study:
 
Exclusion Criteria after Screening
 
The subject must not:
 
1. Be currently pregnant or lactating.2. Be currently using any ocular medications or have any ocular infection of any type.3. By self-report, have any ocular or systemic disease, allergies, infection, or use of medication that the investigator believes might contraindicate or interfere with contact lens wear, or otherwise compromise study endpoints, including infectious disease (e.g., hepatitis, tuberculosis), contagious immunosuppressive disease (e.g., Human Immunodeficiency Virus [HIV]), autoimmune disease (e.g. rheumatoid arthritis, Sjögren's syndrome), or history of serious mental illness or seizures. See section 9.1 for additional details regarding excluded systemic medications.4. Have habitually worn rigid gas permeable (RGP) lenses, orthokeratology lenses, or hybrid lenses (e.g. SynergEyes, SoftPerm) within the past 6 months.5. Be currently wearing monovision or multifocal contact lenses.6. Be currently wearing lenses in an extended wear modality.7. Have participated in a contact lens or lens care product clinical trial within 30 days prior to study enrollment.8. Be an employee (e.g., Investigator, Coordinator, Technician) or immediate family member of an employee (including partner, child, parent, grandparent, grandchild or sibling of the employee or their spouse) of the clinical site. 
Exclusion Criteria at Baseline Evaluation
 
The subject must not:
 
9. Have clinically significant (grade 3 or higher on the FDA grading scale) slit lamp findings (e.g., corneal edema, neovascularization or staining, tarsal abnormalities or bulbar injection) or other corneal or ocular disease or abnormalities that the investigator believes might contraindicate contact lens wear or may otherwise compromise study endpoints (including entropion, ectropion, chalazia, recurrent styes, glaucoma, history of recurrent corneal erosions, aphakia, moderate or above
----------------------------------	---

[figure not shown]
Clinical Study Protocol
Johnson & Johnson Vision Care, Inc.

	
corneal distortion, herpetic keratitis). (Specify method of determination if needed).
 
10. Have a history of strabismus or amblyopia.
 
11. Have fluctuations in vision due to clinically significant dry eye or other ocular conditions.
 
12. Have had or have planned (within the study period) any ocular or intraocular surgery (e.g., radial keratotomy, PRK, LASIK, iridotomy, retinal laser photocoagulation, etc.).

Disallowed Medications/Interventions	
No ocular medications.
 
See section 9.1 for details regarding disallowed systemic medications.

Measurements and Procedures	Subjects will respond to a GSI/MRD questionnaire.
Microbiology or Other Laboratory Testing	None
Study Termination	The occurrence of an Unanticipated Adverse Device Effect (UADE) or Serious Adverse Event (SAE) for which a causal relationship to a test article cannot be ruled out, will result in stopping further dispensing investigational product. In the event of a UADE or SAE, the Sponsor Medical Monitor may unmask the treatment regimen of subject(s) and may discuss this with the Principal Investigator before any further subjects are enrolled.
Ancillary Supplies/ Study-Specific Materials	RevitaLens, preservative-free artificial tears.
Principal Investigator(s) and Study Institution(s)/Site(s)	A full list of Principal Investigators, clinical sites, and institutions is kept separately from the Study Protocol and is included in the study Trial Master File.

Clinical Study Protocol

Johnson & Johnson Vision Care, Inc.

Figure 1: Study Flowchart

Clinical Study Protocol

Johnson & Johnson Vision Care, Inc.

COMMONLY USED ABBREVIATIONS, ACRONYMS AND DEFINITIONS OF TERMS

ADE	Adverse Device Effect
ADHD	Attention Deficit Hyperactivity Disorder
AE	Adverse Event/Adverse Experience
BSCVA	Best Spectacle Corrected Visual Acuity
CFR	Code of Federal Regulations
CLUE	Contact Lens User Experience
COM	Clinical Operations Manager
CRA	Clinical Research Associate
CRF	Case Report Form
CRO	Contract Research Organization
	
D	Diopter
DMC	Data Monitoring Committee
eCRF	Electronic Case Report Form
EDC	Electronic Data Capture
ETDRS	Early Treatment Diabetic Retinopathy Study
FDA	Food and Drug Administration
GCP	Good Clinical Practice
HEV	High Energy Visible light
HIPAA	Health Insurance Portability and Accountability Act
HIV	Human Immunodeficiency Virus
IB	Investigator's Brochure
ICH	The International Council for Harmonization
IDE	Investigational Device Exemption
IEC	Independent Ethics Committee
IRB	Institutional Review Board
ISO	International Organization for Standardization
ITT	Intent-to-Treat
JJVC	Johnson & Johnson Vision Care, Inc.
LASIK	Laser-Assisted in Situ Keratomileusis
LogMAR	Logarithm of Minimal Angle of Resolution
OD	Right Eye
OS	Left Eye
OU	Both Eyes
PIG	Patient Instruction Guide
PQC	Product Quality Complaint
PRK	Photorefractive Keratectomy
PRO	Patient Reported Outcome
QA	Quality Assurance
SAE	Serious Adverse Event/Serious Adverse Experience
SAP	Statistical Analysis Plan
SAS	Statistical Analysis System
SD	Standard Deviation
UADE	Unanticipated Adverse Device Effect
UV	Ultraviolet radiation
USADE	Unanticipated Serious Adverse Device Effect
VA	Visual Acuity

Clinical Study Protocol

Johnson & Johnson Vision Care, Inc.

1. INTRODUCTION AND BACKGROUND

This study will investigate the clinical performance of an investigational Test lens against a marketed Control lens.

1.1. Name and Descriptions of Investigational Products

This study will evaluate a senofilcon A-based prototype against a commercially available marketed product Dailies Total 1 (DT1). Further details about the test articles are found in section 6 of this protocol.

1.2. Intended Use of Investigational Products

The intended use of the investigative product is for correcting myopia. During the study, one of the study articles per subject will be worn bilaterally in a daily wear, daily disposable modality for at least 6 hours per day and 5 days per week for approximately two weeks.

1.3. Summary of Findings from Nonclinical Studies

All previous pre-clinical findings were deemed satisfactory prior to proceeding with clinical trials on humans. For the most comprehensive nonclinical information regarding senofilcon A-based investigational lens, refer to the latest version of the Investigator's Brochure.

1.4. Summary of Known Risks and Benefits to Human Subjects

The risks of wearing soft contact lenses are well known and are described in the Investigator's Brochure and Informed Consent. The material safety testing/lens release criteria was determined based on the Risk Assessment. Benefits to the subjects include the correction of their refractive error.

For the most comprehensive risk and benefit information regarding senofilcon A-based investigational lens, refer to the latest version of the Investigator's Brochure.

1.5. Relevant Literature References and Prior Clinical Data Relevant to Proposed Clinical Study

The package insert for the DT1 Control lens can be found in the appendices. Prior clinical data of the investigational lens is summarized in the Investigator's Brochure.

The literature is absent of any articles pertaining to the investigational lens. Articles that pertain to the DT1 lenses do exist with a sampling shown here:

1. Wolffsohn, James, et al. "The influence of end of day silicone hydrogel daily disposable contact lens fit on ocular comfort, physiology and lens wettability." *Contact Lens and Anterior Eye* 38.5 (2015): 339-344.
2. Dumbleton, Kathryn A., et al. "A multi-country assessment of compliance with daily disposable contact lens wear." *Contact Lens and Anterior Eye* 36.6 (2013): 304-312.
3. Jayasree, Steph VK, et al. "Quantification of water content in contact lenses combining terahertz imaging and optical coherence tomography." *2021 46th International Conference on Infrared, Millimeter and Terahertz Waves (IRMMW-THz)*. IEEE.

Clinical Study Protocol

Johnson & Johnson Vision Care, Inc.

4. Montés-Micó, Robert, et al. "On-eye optical quality of daily disposable contact lenses for different wearing times." *Ophthalmic and Physiological Optics* 33.5 (2013): 581-591.

2. STUDY OBJECTIVES, ENDPOINTS AND HYPOTHESES

2.1. Objectives

Primary Objective(s)

This study is being conducted to evaluate the clinical performance of an investigational soft contact lens against the clinical performance of a marketed product.

2.2. Endpoints

Primary Endpoint(s):

1. End of day comfort
 - Subjects will respond to the question, "Comfort at the End of the Day" [REDACTED].
 - Response set: Very Satisfied, Satisfied, Neither Satisfied nor Dissatisfied, Dissatisfied, and Very Dissatisfied.

Secondary Endpoint(s):

1. Digital device use
 - Subjects will respond to the question, "Reduction in the feeling of tired eyes from using a computer or other digital device" [REDACTED].
 - Response set: Not Applicable, Excellent, Very Good, Good, Fair, and Poor.
2. Comfort throughout the day
 - Subjects will respond to the question, "I could wear these contact lenses comfortably for as long as I wanted to" [REDACTED].
 - Response set: Strongly Disagree, Disagree, Neither Agree Nor Disagree, Agree, and Strongly Agree.
3. Comfortable vision while night driving
 - Subjects will respond to the question, "Ability to see comfortably while driving at night" [REDACTED].
 - Response set: Not Applicable, Excellent, Very Good, Good, Fair, and Poor.

Other Exploratory Endpoint(s):

Other exploratory endpoints including subjective questions regarding comfort, vision, handling, and preferences, such as:

Clinical Study Protocol

Johnson & Johnson Vision Care, Inc.

1. Clarity of distance vision
 - Subjects will respond to the question, “Clarity of distance vision (i.e. looking at things that are more than 5 feet away, such as street signs)” [REDACTED]
 - Response set: Not Applicable, Excellent, Very Good, Good, Fair, and Poor.
2. Vision clarity throughout the day
 - Subjects will respond to the question, “I was very satisfied by the clarity of my vision throughout the day” [REDACTED]
3. Didn't have to think about the lenses
 - Subjects will respond to the question, “I didn't have to think about my lenses until I was ready to take them out” [REDACTED]
 - Response set: Agree Strongly, Agree Somewhat, Neither Agree Nor Disagree, Disagree Somewhat, and Disagree Strongly.
4. Ability to see comfortably using digital devices
 - Subjects will respond to the question, “Ability to see comfortably while using a computer or other digital device” [REDACTED]
 - Response set: Not Applicable, Excellent, Very Good, Good, Fair, and Poor.
5. Tired eyes
 - Subjects will respond to the question, “My eyes felt tired” [REDACTED]
6. Eye fatigue
 - Subjects will respond to the question, “Eye fatigue” [REDACTED]
Response set: Always, Frequently, Occasionally, Rarely, Never, and Don't Know.
7. Vision at the end of the day
 - Subjects will respond to the question, “I had very good vision at the end of the day” [REDACTED]
8. Vision in dim lighting
 - Subjects will respond to the question, “I was satisfied with the quality of my vision in dim lighting” [REDACTED]
9. Dry eyes at the end of the day
 - Subjects will respond to the question, “I have experienced dry eyes at the end of the day” [REDACTED]

Response set for CLUE items: Strongly Disagree, Disagree, Neither Agree Nor Disagree, Agree, and Strongly Agree. [REDACTED] also has a “Not Applicable” response option.

2.3. Hypotheses

The primary hypothesis must be met for the objective of this study to be satisfied:

Clinical Study Protocol

Johnson & Johnson Vision Care, Inc.

Primary Hypothesis

1. After approximately two weeks of wear, the Test lens will have superior performance to the Control lens with respect to end of day comfort.

The primary hypothesis must be met in order to begin testing any secondary hypotheses.

Secondary Hypotheses

1. After approximately two weeks of wear, the Test lens will have superior performance to the Control lens with respect to digital device use.
2. After approximately two weeks of wear, the Test lens will have superior performance to the Control lens with respect to comfort throughout the day.
3. After approximately two weeks of wear, the Test lens will have superior performance to the Control lens with respect to comfortable vision while night driving.

Exploratory Hypotheses

There will be no exploratory hypotheses. All exploratory endpoints will be descriptively summarized.

3. TARGETED STUDY POPULATION

3.1. General Characteristics

Approximately 180 subjects will be targeted to the Test Group and approximately 180 will be targeted to the Control Group. Within each lens group, the intent is to complete 165 (330 total subjects). Enrolled subjects will be habitual wearers of silicone hydrogel spherical contact lenses. All subjects will be the age of ≥ 18 and < 40 . Subjects will wear the study contact lenses approximately two weeks each on a daily wear (DW) daily disposable (DD) basis for a total study duration of approximately 14 days (2 weeks) per subject.

3.2. Inclusion Criteria

Potential subjects must satisfy all of the following criteria to be enrolled in the study:

Inclusion Criteria after Screening

The subject must:

1. Read, understand, and sign the STATEMENT OF INFORMED CONSENT and receive a fully executed copy of the form.
2. Appear able and willing to adhere to the instructions set forth in this clinical protocol.
3. Be between 18 and 39 (inclusive) years of age at the time of screening.
4. By self-report, habitually wear spherical soft silicone hydrogel contact lenses in both eyes in a daily wear or daily disposable wear modality (i.e. not extended wear

Clinical Study Protocol

Johnson & Johnson Vision Care, Inc.

modality). Habitual wear is defined as a minimum of 6 hours of wear per day, for a minimum of 5 days per week during the past 30 days.

5. Have a habitual contact lens prescription that is current within the prior 6 months, and they must have worn that prescription for at least 2 weeks prior to entering the study.
6. Possess a wearable pair of spectacles that provide correction for distance vision.

Inclusion Criteria at Baseline Evaluation

7. The spherical equivalent of the subject's vertex-corrected distance refraction must be between -1.00 and -6.00 DS (inclusive) in each eye.
8. The magnitude of the cylindrical component of the subject's vertex-corrected distance refraction must be between 0.00 and 1.00 DC (inclusive) in each eye.
9. The best corrected, monocular, distance visual acuity must be 20/25 or better in each eye.

3.3. Exclusion Criteria

Potential subjects who meet any of the following criteria will be excluded from participating in the study:

Exclusion Criteria after Screening:

The subject must not:

1. Be currently pregnant or lactating.
2. Be currently using any ocular medications or have any ocular infection of any type.
3. By self-report, have any ocular or systemic disease, allergies, infection, or use of medication that the investigator believes might contraindicate or interfere with contact lens wear, or otherwise compromise study endpoints, including infectious disease (e.g., hepatitis, tuberculosis), contagious immunosuppressive disease (e.g., Human Immunodeficiency Virus [HIV]), autoimmune disease (e.g. rheumatoid arthritis, Sjögren's syndrome), or history of serious mental illness or seizures. See section 9.1 for additional details regarding excluded systemic medications.
4. Have habitually worn rigid gas permeable (RGP) lenses, orthokeratology lenses, or hybrid lenses (e.g. SynergEyes, SoftPerm) within the past 6 months.
5. Be currently wearing monovision or multifocal contact lenses.
6. Be currently wearing lenses in an extended wear modality.
7. Have participated in a contact lens or lens care product clinical trial within 14 days prior to study enrollment.
8. Be an employee (e.g., Investigator, Coordinator, Technician) or immediate family member of an employee (including partner, child, parent, grandparent, grandchild or sibling of the employee or their spouse) of the clinical site.

Clinical Study Protocol

Johnson & Johnson Vision Care, Inc.

Exclusion Criteria at Baseline Evaluation

The subject must not:

9. Have clinically significant (grade 3 or higher on the FDA grading scale) slit lamp findings (e.g., corneal edema, neovascularization or staining, tarsal abnormalities or bulbar injection) or other corneal or ocular disease or abnormalities that the investigator believes might contraindicate contact lens wear or may otherwise compromise study endpoints (including entropion, ectropion, chalazia, recurrent styes, glaucoma, history of recurrent corneal erosions, aphakia, moderate or above corneal distortion, herpetic keratitis).
10. Have a history of strabismus or amblyopia.
11. Have fluctuations in vision due to clinically significant dry eye or other ocular conditions.
12. Have had or have planned (within the study period) any ocular or intraocular surgery (e.g., radial keratotomy, PRK, LASIK, iridotomy, retinal laser photocoagulation, etc.)

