5. TEST ARTICLE ALLOCATION AND MASKING

5.1. Test Article Allocation

Use of the test articles will be randomized using a lens fitting schedule supplied by the study biostatistician. The clinical site will follow the lens fitting schedule provided and will complete enrollment according to the randomization list and will not pre-select or pre-assign subjects.

Randomly-permuted block randomization will be used to avoid bias in the assignment of subjects to treatment and to enhance the validity of statistical comparisons across treatment groups. A computer-generated randomization scheme will be used to randomly assign subjects to one of the two lens groups (Test or Control). The randomization will be stratified by site and type of habitual lens wear (daily disposable and daily wear reusable). The ratio of habitual wearers of daily disposable lenses to habitual wearers of daily wear reusable lenses is 7:3 within each study site (7 habitual wearers of daily disposable lenses versus 3 habitual wearers of daily wear reusable lenses). See Table 1. The random scheme will be generated using the PROC PLAN procedure from Statistical Analysis System (SAS) Software Version 9.4 or higher (SAS Institute, Cary, NC).⁵

Randomization will be performed at Visit 1. The following must have occurred prior to randomization:

- Informed consent must have been obtained.
- The subject must have met all eligibility criteria.
- The subject's screening and baseline information must have been collected.

When dispensing test articles, the following steps should be followed to maintain randomization codes:

1. Investigator or designee (documented on the Delegation Log) will consult the lens fitting schedule to obtain the test article assignment for that subject prior to dispensing.
2. Investigator or designee will record the subject's number on the appropriate line of the lens fitting schedule.
3. Investigator or designee will pull the appropriate test articles from the study supply. All test articles that are opened, whether dispensed (placed/fit on eye or dispensed outside the clinical site) or not, must be recorded on the Test Article Accountability Log in the "Dispensed" section.

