10. DEVIATIONS FROM THE PROTOCOL

Investigator will notify study sponsor upon identification of a protocol deviation. Protocol deviations must be reported to the sponsor within 24 hours after discovery of the protocol deviation. The Investigator will report deviations per IRB/IEC requirements. All deviations will be tracked, and corrective actions implemented as appropriate.

If it becomes necessary for the Investigator to implement a deviation in order to eliminate an immediate hazard to the trial subject, the Investigator may implement the deviation immediately without notification to the sponsor. Within 24 hours after the implemented deviation, the Investigator must notify and provide the rationale to the Sponsor and, as required, to the IEC/IRB.

If the deviation potentially impacts the safety of patient or changes the technical integrity of the study, then it must be reported to IEC/IRB. This is a "Major Deviation". Deviations that contradict the information contained in the Informed Consent/Assent forms will be considered Major Deviations.

Minor deviations have no substantive effect on patient safety or technical integrity of the study. They are often logistical in nature.

Protocol waivers are prohibited.

Table 8 lists examples of deviations that will constitute major and minor protocol deviations for this study.

Clinical Study Protocol
Johnson & Johnson Vision Care, Inc.

Table 8: Examples of major and minor protocol deviations

Deviation category	Major deviation	Minor deviation
Out-of-window visit	Visit attended 2 days or more than out of visit window defined in study procedures	Visit attended 1 day or fewer out of visit window defined in study procedures
Unanswered PRO questions	For questionnaires where data is related to a primary or secondary endpoint, 2 or more PRO questions are unanswered (i.e., left blank).	For questionnaires where data is related to a primary or secondary endpoint, 1 or fewer PRO questions are unanswered (i.e., left blank). For questionnaires where data where data is not related to a primary or secondary endpoint, any PRO questions are unanswered (i.e., left blank).
Insufficient wear of study lenses	Subject does not wear study lenses for at least 6 hours on at least 5 days of a study lens wear period.	NA

In the case of a major protocol deviation, the decision of whether or not the subject will be excluded from the Per-Protocol analysis population will be made at the time of cohort review.

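### Synopsis and body disagree on the prior-trial exclusion window (30 or 14 days) and on what must follow an SAE whose relation to the lens cannot be ruled out

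*Combined protocol and SAP*

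**What the plan says.** **Prior participation in a trial.** Section 3.3, exclusion 7: "Have participated in a contact lens or lens care product clinical trial within 14 days prior to study enrollment". Synopsis, exclusion 7: "Have participated in a contact lens or lens care product clinical trial within 30 days prior to study enrollment". Only the number differs. The synopsis does not summarise the criteria; it reproduces the numbered list under the same binding introduction.

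Section 5.1 makes eligibility a condition of randomisation: "The subject must have met all eligibility criteria". Section 10 closes the other route: "Protocol waivers are prohibited".

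**After an SAE that may be related.** The Study Termination row of the synopsis says that an SAE whose causal link to a test article cannot be excluded "will result in stopping further dispensing investigational product". It adds that the Sponsor Medical Monitor "may discuss this with the Principal Investigator before any further subjects are enrolled". Section 11 covers the same kind of event with the verbs exchanged: the event *may* lead to dispensing being halted, and the sponsor *will* discuss it with the investigator before enrolment goes on. Both texts say that the sponsor side *may* unmask.

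The companion trigger is called UADE in the synopsis and USADE in section 11. Section 13.1 defines only UADE.

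**The concern.** Both rules are operative text, and each is stated twice with a different content. A reader cannot tell which statement binds.

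For exclusion 7 the exposure falls on the sites. A site that screens by section 3.3 could randomise someone 20 days out of another trial and be cited under the synopsis; a site that screens by the synopsis would turn the same person away. There are 18 to 20 sites, they recruit partly from their own subject databases (section 3.4), and section 20 lets the sponsor withhold payment for continuing an ineligible subject.

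For the safety rule the exposure falls mainly on the sponsor. Serious events reach the sponsor within 24 hours (section 13.4.1), and the protocol should then say whether dispensing has to stop and whether the investigator has to be consulted before more subjects enter. As written it answers each question both ways. There is no data monitoring committee (section 16.4), so the written rule carries more weight.

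**Working it through.** The point rests on comparing text. The plan states no figure for either rule.

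**1. Width of the eligibility conflict.** Inputs: 30 days (synopsis) and 14 days (section 3.3). Reading each window as including its last day, the difference is 30 − 14 = 16 days, that is, days 15 to 30.

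| Days since the other trial | Synopsis | Section 3.3 |
|---|---|---|
| 1–14 | excluded | excluded |
| 15–30 | excluded | not excluded by item 7 |
| 31 or more | not excluded by item 7 | not excluded by item 7 |

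**2. Do the neighbouring criteria show which number was meant?** No. Inclusion 4 looks back 30 days ("minimum of 5 days per week during the past 30 days"), while inclusion 5 uses two weeks ("they must have worn that prescription for at least 2 weeks prior to entering the study"). Each candidate window has a neighbour that matches it.

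**3. Do those criteria empty the 15–30 day band?** Not by logic. Inclusion 4 asks for spherical silicone hydrogel wear but not for one brand, and inclusion 5 asks for only two weeks in the current prescription. Someone who left a silicone hydrogel or lens care trial 20 days ago could meet both, provided any trial lenses worn in the look-back period count towards habitual wear, which the protocol does not address. Others in the band would fail one or the other.

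**4. The safety rule, step by step.**

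| Step | Synopsis | Section 11 | Agree? |
|---|---|---|---|
| Stop dispensing | will | may | no |
| Unmask | may | may | yes |
| Discuss with the investigator before further enrolment | may | will | no |

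Two of three steps conflict. The triggers need care. In both texts the stop sentence concerns an SAE not ruled out as related, alongside the unanticipated device effect. The sentence on unmasking and discussion concerns any SAE. An SAE not ruled out as related meets both triggers in both texts, so all three steps apply to it.

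**5. Does anything else in section 11 settle it?** No. Its separate rule suspends the study once more than two subjects in the investigational group have serious device-related events. That leaves open what follows a first such event. The list of ocular SAEs in section 13.1 includes iritis and microbial keratitis, so the trigger is not confined to unanticipated events.

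**6. Is there a rule of precedence?** None was found in the text available for review, and the visible change entry for version 3.0 deals only with the enrolment figures and the number of sites.

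**7. Effect on the sample size.** None. Table 10 reproduces from its stated proportions and alpha levels with the pooled-variance test for two proportions: 126, 153, 153 and 165 per arm at 90% power. Neither rule enters that calculation.

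**The case against.** The best case on the other side has five parts.

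- **The safety texts do not impose opposing duties.** What *will* requires, *may* permits, so a sponsor that always took the stricter step would satisfy both. This is correct, but nothing instructs the sponsor to do so, and whether each step is compulsory remains unanswered.
- **The sponsor decides in any case.** Section 11 reserves to the sponsor the decision when a study is stopped. That general power does not turn a stated obligation into an option, or the reverse.
- **The clauses are not exact counterparts.** The synopsis speaks of investigational product and the Sponsor Medical Monitor; section 11 speaks of test article, which can include the control lens, and of the Sponsor. This stands as a description, but the conflict over dispensing the Test lens remains.
- **UADE and USADE are one concept.** The abbreviation list expands USADE, the heading in section 13.4.1 joins the two, and the UADE definition already requires seriousness. This largely stands. The label is a minor tidying point and carries no weight here.
- **The eligibility conflict has little shown effect.** Inclusions 4 and 5 may remove some of the affected candidates, and the eligibility eCRF, which is not in the documents, may already apply one number at every site. Both are possible. They limit the likely consequence but do not remove the contradiction.

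**Conclusion.** The point holds. The prior-trial window differs by 16 days between two complete statements of the same criterion. For an SAE not ruled out as related, two of three stated steps carry opposite force in the synopsis and section 11. These are contradictions within the protocol's current text.

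The size of the practical effect is unknown: the documents give neither the number of candidates in the 15–30 day band nor an SAE rate, and none is assumed. Type I error, power and the validity of the randomised comparison are unaffected. The consequences are for eligibility decisions, deviation reporting and the clarity of the safety response. It should be corrected, but it does not threaten the primary analysis.

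The conclusion assumes that the pages not available for review, such as title, signature and consent pages, contain no rule of precedence. A clause there stating that the body governs would settle both conflicts in principle, though the synopsis would still need correcting.

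**What to change.** - **Exclusion 7:** the sponsor should choose one window, state it in both the synopsis and section 3.3, and confirm that the eligibility eCRF uses it. If subjects have already been randomised, check whether any fell in the 15–30 day band.
- **Safety action:** reconcile the synopsis row with section 11, so that one trigger, under one label defined in section 13.1, leads to one stated action on dispensing and one stated step before further enrolment. Name the same responsible party and the same product term in both places.
- **Precedence:** a sentence saying which part governs would cover any mismatch that remains.

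Which window and which safety rule to adopt is for the sponsor; no recommendation is made here. The cost is a few lines in two places for each rule, plus the eCRF check, and it can go into any amendment. Sample size, alpha and analysis do not change.
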